8.2.4. Secondary Efficacy Analyses

8.2.4.1. The 7-day Point-prevalence of Smoking Abstinence at Weeks 12, 24, and 52

The 7-day point prevalence of abstinence will be summarized by treatment group and visit from Week 3 through Week 52 using descriptive statistics and bar charts.

These will be summarized for the following groups:

- Overall study.
- 12-16 year old age stratum.
- 12-16 year old age stratum, ≤ 55 kg weight stratum.
- 12-16 year old age stratum, > 55 kg weight stratum.
- 17-19 year old age stratum.

The 7-day point prevalence of abstinence at Weeks 12, 24, and 52 will be analyzed using separate logistic regression models as described in [Section 8.1.1.2](#). Odds ratios and 95% confidence intervals will be shown in plots.

These will be analysed for the following groups:

- Overall study.
- 12-16 year old age stratum (without age strata covariate).
- 12-16 year old age stratum, ≤ 55 kg weight stratum (without age strata or body weight strata covariates).
- 12-16 year old age stratum, > 55 kg weight stratum (without age strata or body weight strata covariates).

8.2.4.2. The Reduction in Number of Cigarettes Smoked at Weeks 12, 24, and 52

The reduction in the number of the cigarettes smoked will be calculated at each visit by subtracting the reported average number of cigarettes smoked per day in the past 7 days at each visit from the average number of cigarettes smoked per day in the past 7 days reported at the baseline visit.

The reduction in the mean number of cigarettes smoked per day over the past 7 days will be summarized by treatment group and visit using descriptive statistics.

These will be summarized for the following groups:

- Overall study.
- 12-16 year old age stratum.
- 12-16 year old age stratum, ≤ 55 kg weight stratum.
- 12-16 year old age stratum, > 55 kg weight stratum.
- 17-19 year old age stratum.

The reduction in the mean number of cigarettes smoked per day will be analyzed using longitudinal repeated measures models as described in [Section 8.1.2.2](#). In addition to treatment and visit, baseline number of cigarettes smoked, pooled study center, age strata, and body weight strata will be included as covariates. A treatment by visit interaction will be included for estimation purposes. Least square means and 95% confidence intervals will be shown in plots.

These will be analysed for the following groups:

- Overall study.
- 12-16 year old age stratum (without age strata covariate).
- 12-16 year old age stratum, ≤ 55 kg weight stratum (without age strata or body weight strata covariates).
- 12-16 year old age stratum, > 55 kg weight stratum (without age strata or body weight strata covariates).

8.2.4.3. The Continuous Abstinence Rate from Week 9 through Week 24 and Week 52

The continuous abstinence rate at a given time point will be defined as the proportion of subjects who remained abstinent from Week 9 through the time point being summarized.

The continuous abstinence rates from Week 9 through Week 24 and Week 9 through Week 52 will be summarized by treatment group using descriptive statistics and bar charts.

These will be summarized for the following groups:

- Overall study.
- 12-16 year old age stratum.
- 12-16 year old age stratum, ≤ 55 kg weight stratum.
- 12-16 year old age stratum, > 55 kg weight stratum.

- 17-19 year old age stratum.

The continuous abstinence from Week 9 through Week 24 and from Week 9 through Week 52 endpoints will be analyzed using separate logistic regression models as described in [Section 8.1.1.2](#). Odds ratios and 95% confidence intervals will be shown in plots.

These will be analysed for the following groups:

- Overall study.
- 12-16 year old age stratum (without age strata covariate).
- 12-16 year old age stratum, ≤ 55 kg weight stratum (without age strata or body weight strata covariates).
- 12-16 year old age stratum, > 55 kg weight stratum (without age strata or body weight strata covariates).

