The primary analysis population will be all subjects who took at least one dose of randomized study medication. All significance tests will be two-sided and will use a 0.05 significance level. No adjustments will be made to the nominal p-values for analysis of the multiple efficacy endpoints. Subjects who discontinue the study will be considered smokers for the remainder of the study regardless of their last smoking status evaluation.

For the binary endpoints with planned inferential treatment comparisons, a logistic regression model will be fitted which will include the main effects of strata, treatment group and center as independent variables. Treatment by center interaction will be investigated by an expanded model; however the reported p-values will be based on the main effects model. Analysis of the change from baseline in mean number of cigarettes smoked per day will use analysis of covariance with baseline value, strata, treatment group and center included in the model. The assumptions of the linear model will be examined and if not satisfied, nonparametric methods will be used. There will be no formal inferential analyses of safety assessments. The standard and additional safety data will be summarized by treatment group using descriptive statistics.

Table 1. SCHEDULE OF ACTIVITIES

Protocol Activity	SCR	BL	Wk 1	Wk 2	Wk 3	Wk 4	Wk 5	Wk 6	Wk 7	Wk 8	Wk 9	Wk 10	Wk 11	Wk 12	ET 12
Informed consent	X														
Medical history	X														
Physical examination	X														
Body Weight and Height (triplicate)	X	X												X	X
Tobacco use history	X														
Nicotine dependence: FTND	X														
Randomization		X													
Target Quit Date (TQD)			X												
Urine Pregnancy test ^a	X	X			X			X			X			X	X
Urine drug test (dipstick at site)	X	X			X			X			X			X	X
Vital Signs (BP/PR)	X	X	X	X	X	X	X	X	X	X	X	X	X	X	X
Concomitant Medications	X	X	X	X	X	X	X	X	X	X	X	X	X	X	X
Non-drug treatment	X	X	X	X	X	X	X	X	X	X	X	X	X	X	X
Hematology & Chemistry	X				X			X						X	X
Pharmacokinetic samples ^b					X			X						X	X
Dispense Medication		X	X	X	X	X	X	X	X	X	X	X	X		
Dosing Record			X	X	X	X	X	X	X	X	X	X	X	X	X
SBQ-R	X														
C-SSRS	X	X	X	X	X	X	X	X	X	X	X	X	X	X	X
HADS	X	X	X	X	X	X	X	X	X	X	X	X	X	X	X
Adverse Event Monitoring		X	X	X	X	X	X	X	X	X	X	X	X	X	X
Neuropsychiatric Adverse Event Interview (NAEI)		X	X	X	X	X	X	X	X	X	X	X	X	X	X
Nicotine Use Inventory		X	X	X	X	X	X	X	X	X	X	X	X	X	X
Review/distribute Smoking Diary worksheet	X	X	X	X	X	X	X	X	X	X	X	X	X	X	X

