9.1.2. Analysis of Secondary Endpoints

9.1.2.1. Efficacy Endpoints

There are several secondary smoking abstinence endpoints for this study, as indicated in Section 2.2. Each of these binary secondary endpoints will be analyzed using procedures similar to that described above for the primary efficacy endpoint. All statistical tests will be two-sided and at a 0.05 level of significance. P-values will be reported with no adjustments for the analysis of multiple secondary endpoints.

The number of cigarettes smoked over the past seven days will be collected by completion of the NUI at each visit. The reduction in the number of the cigarettes smoked will be calculated at each visit by subtracting the reported number of cigarettes smoked in the past 7 days at each visit from the number of cigarettes smoked in the past 7 days reported at the baseline visit. Longitudinal repeated measures models including strata, treatment, center,

and baseline number of cigarettes smoked will be used to assess the effect of treatment on the reduction in the number of cigarettes smoked.

Pharmacokinetic Endpoints

The plasma concentration-time data collected in this study will be analyzed via nonlinear mixed effects (NONMEM software) to describe the population pharmacokinetics (PK) of varenicline including an assessment of covariate effects in adolescent smokers.

Varenicline exposure data derived from the individual Bayesian estimates of the pharmacokinetic parameters will be subsequently utilized to characterize the population exposure-response relationships for selected measures of efficacy and safety/tolerability of varenicline in this pediatric population. Model development may require the use of data from previous clinical studies. An analysis plan describing the details of the model building, covariate assessment and model validation will be provided separately before the unblinding of the data.

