Appendix 1. Nicotine Use Inventory

Asked at the Week 1 visit through the Week 12 visit

- Has the subject smoked any cigarettes (even a puff) since the last study visit?
- Has the subject used any other nicotine-containing products (eg, nicotine patch, nicotine gum, nicotine nasal spray, nicotine inhaler, nicotine lozenge, pipe, cigars, chew, snuff) since the last study visit?
- Has the subject smoked any cigarettes (even a puff) in the last 7 days?
- If the subject smoked in the last 7 days, has the subject had any days on which no cigarettes were smoked, and if so, how many days?
- If the subject smoked in the last 7 days, how many cigarettes did the subject smoke per day, on average for the days on which smoking occurred?
- Has the subject used any other nicotine-containing products (eg, nicotine patch, nicotine gum, nicotine nasal spray, nicotine inhaler, nicotine lozenge, pipe, cigars, chew, snuff) in the last 7 days?

Asked at the Week 13 visit through the Week 52 visit

- Has the subject smoked any cigarettes (even a puff) since the last contact?
- Has the subject used any other tobacco products (eg, pipe, cigars, chew, snuff) since the last contact?
- Has the subject smoked any cigarettes (even a puff) in the last 7 days?
- If the subject smoked in the last 7 days, has the subject had any days on which no cigarettes were smoked, and if so, how many days?
- If the subject smoked in the last 7 days, how many cigarettes did the subject smoke per day, on average for the days on which smoking occurred?
- Has the subject used any other tobacco products (eg, pipe, cigars, chew, snuff) in the last 7 days?

Additionally Asked on the Week 52 visit

- Has the subject smoked any cigarettes (even a puff) in the last 4 weeks?
- Has the subject used any other tobacco products (eg, pipe, cigars, chew, snuff) in the last 4 weeks?
- Nicotine replacement therapy and/or other smoking cessation medications should be recorded in the concomitant medicine pages in the case report form.

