6. ENDPOINTS AND COVARIATES

6.1. Efficacy Endpoint(s)

Efficacy assessments will include measurement of smoking cessation and reduction obtained from the Nicotine Use Inventory (NUI) and urine cotinine measurements. The Week 24, 32, 40, and 48 visits are telephone visits, and therefore do not include collection of urine cotinine. Abstinence rates based on or including these visits do not require chemical confirmation. Urine cotinine is collected at all in-person clinic visits, and all abstinence rates based on in-clinic visits utilize urine cotinine to confirm abstinence. The reduction in the number of cigarettes smoked is based solely on the reported number of cigarettes on the NUI at baseline and the post-baseline visit of interest. The endpoints derived from these include:

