7. HANDLING OF MISSING VALUES

Subjects who discontinue the study will be considered smokers for the remainder of the study regardless of their last smoking status evaluation. This implies that subjects who discontinue will continue to be represented in the denominator but not in the numerator regardless of smoking status at the time of discontinuation. This can be considered a worst case carried forward analysis and represents a conservative approach to imputation of missing data.

For the HADS-A and HADS-D, if more than one question within a domain (anxiety or depression) is missing, the score will be set to missing. If only one question is missing, the missing response will be imputed with the domain-specific mean based on the remaining questions.

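### Is the cigarette-reduction endpoint left undefined because the Nicotine Use Inventory does not ask for a seven-day average?

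*SAP*

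**What the plan says.** Reduction in cigarettes smoked at Weeks 12, 24 and 52 is a secondary endpoint. The relevant statements are:

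- **SAP 8.2.4.2** obtains the reduction by "subtracting the reported average number of cigarettes smoked per day in the past 7 days at each visit" from the corresponding baseline figure. Its next sentence again describes a daily mean over seven days.
- **SAP 6.1** gives the source: "The reduction in the number of cigarettes smoked is based solely on the reported number of cigarettes on the NUI at baseline" and at the later visit of interest.
- **Protocol 9.1.2.1** works in seven-day numbers. It says "The number of cigarettes smoked over the past seven days will be collected by completion of the NUI at each visit", and it forms the reduction by "subtracting the reported number of cigarettes smoked in the past 7 days at each visit" from the baseline number.
- **Protocol Summary, Statistical Methods** uses a per-day scale: "Analysis of the change from baseline in mean number of cigarettes smoked per day will use analysis of covariance".
- **Protocol Appendix 1** lists the NUI items from Week 1 onward. After a yes/no item on any smoking in the last seven days, those who smoked are asked "has the subject had any days on which no cigarettes were smoked, and if so, how many days" and then "how many cigarettes did the subject smoke per day, on average for the days on which smoking occurred".
- **SAP 7** says "Subjects who discontinue the study will be considered smokers for the remainder of the study regardless of their last smoking status evaluation". It then covers missing HADS items and says nothing about cigarette counts.

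**The concern.** Both documents call the figure reported, yet no listed NUI item reports a seven-day average or a seven-day number. The only amount asked for is an average over smoking days. If a programmer put that answer straight into the subtraction, a subject who cut down by smoking on fewer days would show little or no reduction, or even an increase. Subjects who did not smoke in the last seven days skip the amount item. If they were treated as missing, the repeated measures model would lose the best responders, and more of them in the better arm. The protocol and SAP also differ in unit by a factor of 7. At stake is one secondary endpoint at three time points. The primary endpoint and the abstinence endpoints do not use the count. Baseline cigarettes also enter the multiple-imputation sensitivity analysis of the primary endpoint in SAP 8.2.3, but only as a predictor.

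**Working it through.** The documents state no effect size or power for this endpoint, so there is no planned figure to reproduce. The check is whether the collected items determine the quantity the SAP defines.

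**Inputs (Protocol Appendix 1).** Let c be cigarettes per day on smoking days and s the smoke-free days among the last seven. Both are asked only if the subject smoked in the last seven days.

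**Derivation.**

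- Seven-day number (Protocol 9.1.2.1): c × (7 − s).
- Seven-day daily average (SAP 8.2.4.2): c × (7 − s)/7.
- If the subject reports not even a puff in seven days, both are 0. This is a known value and not a missing one.

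The unconverted answer c equals the SAP quantity only when s = 0.

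**Size of the error if c were used unconverted.** Assume a baseline of 10 a day on all seven days and c = 6 at the visit. Unconverted, the reduction is 10 − 6 = 4.00 whatever s is.

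| s | 6 × (7 − s)/7 | Reduction per day | Reduction in seven-day number |
|---|---|---|---|
| 0 | 6.00 | 4.00 | 28 |
| 2 | 4.29 | 5.71 | 40 |
| 5 | 1.71 | 8.29 | 58 |
| 6 | 0.86 | 9.14 | 64 |

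The sign can also change. From 10 a day on seven days to 12 a day on two days, the unconverted result is −2, while the SAP quantity is 10 − 24/7 = 6.57.

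For a subject who smoked daily at baseline, the error is c × s/7. It is therefore small when few cigarettes are smoked per smoking day. For s from 1 to 6 it is 0.14 to 0.86 a day at c = 1, and 0.29 to 1.71 at c = 2. The entry minimum of 5 a day is an average over the 30 days before entry. It sets no floor on c after the quit date.

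**Zero rule.** For illustration, borrow the planning rates in Protocol 9.1 (9% and 24%) as abstinent shares. Assume a baseline of 10 a day and the same mean reduction r among smokers in both arms. Scoring abstainers as 0 gives a between-arm difference of (0.24 − 0.09) × (10 − r): 1.20, 0.90 or 0.60 a day for r = 2, 4 or 6. Dropping abstainers gives 0 in a simple comparison of observed means. The choice would matter, but the form leaves only one defensible value.

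**Unit.** The Protocol 9.1.2.1 number is exactly 7 times the SAP average, as the last two columns show apart from rounding. If the outcome and the baseline covariate are both multiplied by 7, the treatment estimate and its standard error are too. Test statistics and p-values do not change.

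**Cotinine-positive subjects who deny smoking.** SAP 8.2 classes them as smokers for abstinence. SAP 6.1 takes the reduction from the NUI answer alone, so their count stays as reported.

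**The case for a change.** The strongest case for a change is that a pre-specified endpoint should not rely on a programmer's good sense. The word reported points to an item on the form, and the only amount on the form is the smoking-day average. Cutting down by smoking on fewer days is a plausible response in a cessation trial. One sentence would remove the ambiguity, and neither definition refers the reader to another document.

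Some of this stands. Neither supplied document prints the conversion or the zero. Appendix 1 lists no baseline item set, although the NUI is completed at baseline, so the baseline wording cannot be checked.

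It does not show that following the plan leads to a wrong result. The SAP states the averaging period twice, and a smoking-day average is not an average over seven days. The smoke-free-days item comes immediately before the amount item and supplies the missing factor. For the error to occur, an analyst would have to disregard the stated period, ignore that adjacent item and treat reported non-smoking as missing. Protocol 9 also assigns detailed methodology to a Statistical Rulebook as well as the SAP. That document was not supplied, and a variable-level derivation could well be there.

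**Conclusion.** The concern does not call for a change. The SAP defines the target as the daily average over the past seven days, and from Week 1 on the NUI determines it exactly: c × (7 − s)/7, or 0 when no smoking is reported. An analyst who follows the definition will get there. The protocol's seven-day number is a clerical difference in unit with no effect on any test. The per-subject errors shown above are real only under a reading that contradicts the SAP, and they rest on assumed smoking patterns. The documents show no effect on the treatment comparison. The conclusion assumes that the baseline NUI carries the same items, or otherwise yields a seven-day average, which analysts would confirm when they program the variable.

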8.2.5. Additional Efficacy Analysis

Subjects who reported using any non-study smoking cessation aids during the non-treatment follow-up period will be displayed in a table described in [Section 8.1.1.1](#). Additionally, this subset of concomitant medication use will be listed in a separate listing.

8.2.6. Safety Analysis

All subjects who received at least one dose of study medication will be included in the safety analyses and presentations. All safety data as described in [Section 6.2](#) will be subjected to clinical review and summarized descriptively by treatment group as frequencies of events and mean changes from Baseline, as appropriate.

These will be summarized for the following groups:

- Overall study.
- 12-16 year old age stratum.
- 12-16 year old age stratum, ≤ 55 kg weight stratum.
- 12-16 year old age stratum, > 55 kg weight stratum.
- 17-19 year old age stratum.

8.2.6.1. Adverse Events

The Neuropsychiatric Adverse Event Interview (NAEI) will actively inquire about the following type of adverse events: depression, anxiety, delusions, hallucinations, paranoia, psychosis, mania, panic, agitation, dissociative states, feeling abnormal, hostility, aggression and homicidal ideation. If a subject has a positive response to any item on the NAEI, a

determination will be made by the investigator as to whether this meets criteria for an adverse event. If it does meet criteria as an adverse event it will be recorded on the adverse event pages of the Case Report Form.

All adverse events will be reported using the MedDRA dictionary. The incidence of treatment emergent AEs will be summarized by treatment group and system organ class, higher level group term, and preferred term. Additionally, the incidence of treatment emergent Neuropsychiatric AEs ([Appendix 1](#)) and serious skin adverse events ([Appendix 2](#)), will be summarized by treatment group in separate tables.

Adverse events will be reported according to Pfizer Data Standards (PDS) without consideration of reporting status (volunteered or solicited via the NAEI). Additionally, adverse events will be summarized including only volunteered events. The lag period for this study will be set at 30 days.

CCI [REDACTED]

It should be recognized that most studies are not designed to reliably demonstrate a causal relationship between the use of a pharmaceutical product and an adverse event or a group of adverse events. Except for select events in unique situations, studies do not employ formal adjudication procedures for the purpose of event classification. CCI [REDACTED]

[REDACTED]

CCI [REDACTED]

All adverse event summaries will be produced for the following groups:

- Overall study
- 12-16 year old age stratum
- 12-16 year old age stratum, ≤55 kg weight stratum
- 12-16 year old age stratum, >55 kg weight stratum
- 17-19 year old age stratum

8.2.6.2. Clinical Laboratory Measures

Laboratory abnormalities will be summarized by treatment group according to the following three baseline statuses: Normal Baseline, Abnormal Baseline, and Without Regard to Baseline. Median change from baseline to final observed laboratory data will also be summarized by treatment group. Shift tables from baseline to each assessment will be provided by treatment group.

[REDACTED]

These will be summarized for the following groups:

- Overall study
- 12-16 year old age stratum
- 12-16 year old age stratum, ≤ 55 kg weight stratum
- 12-16 year old age stratum, > 55 kg weight stratum
- 17-19 year old age stratum

8.2.6.3. Vital Signs

Descriptive statistics will be presented by treatment group for pulse, systolic blood pressure, and diastolic blood pressure at baseline and each available visit. Multiple measurements repeated at a given visit will be summarized by the mean of the repeated values. Median changes from baseline in blood pressure and pulse rate will also be presented. Shift tables from baseline to each assessment will be provided by treatment group.

These will be summarized for the following groups:

- Overall study
- 12-16 year old age stratum
- 12-16 year old age stratum, ≤ 55 kg weight stratum
- 12-16 year old age stratum, > 55 kg weight stratum
- 17-19 year old age stratum

8.2.6.4. Height and Weight

As this is a study of adolescents who may still be growing, height will be measured at baseline and Week 12 (or end of treatment) in addition to weight. Descriptive statistics will be presented by treatment group and for height, weight, and body mass index (BMI) at baseline and Week 12. In addition, summary statistics for change from baseline to Week 12 will be displayed for each measure. Multiple measurements repeated at a given visit will be summarized by the mean of the repeated values.

These will be summarized for the following groups:

- Overall study
- 12-16 year old age stratum
- 12-16 year old age stratum, ≤ 55 kg weight stratum

- 12-16 year old age stratum, >55 kg weight stratum
- 17-19 year old age stratum

